3 OBJECTIVES AND ENDPOINTS

| OBJECTIVES | ENDPOINTS | JUSTIFICATION FOR ENDPOINTS |
|---|--|--|
| Primary | | |
| Determine the effect of automated medication adherence platform (HiDO) on medication compliance. | Mean adherence rate to ART in all patients across 90 days (quantified as (n. of doses provided — n. of doses taken) / n. of doses provided x 100) | Adherence data are automatically and continuously recorded by HiDO device, and directly confirmable through manual audit of video recordings. |
| Secondary | | |
| Determine usability of automated medication adherence platform (HiDO), as indicated by user ease of adoption (Time on Task, error rates), standardized user experience metric (SUS), and user endorsement (Net Promoter Score). | 
Measured at Week 2:
 
 • Time on Task for initial registration • Time on Task for “first click” testing • Time on Task for facial recognition setup • Time on Task for medication administration • Number and type of critical and non-critical errors • Error-free rate 
Measured after 90 days use of platform:
 
 • Score on System Usability Scale (SUS) • Net Promoter Score | 
Time on Task and error rates may be compared to published benchmarks for similar platforms.
 
According to usability.gov published by the U.S. Department of Health & Human Services, the SUS is regarded as a reliable tool to assess usability and has become the industry standard.²⁴ Results from the SUS have been published in over 1,300 publications.²⁴ It can be used on small sample sizes with reliable results and can effectively discriminate between usable and unusable systems.
 
The Net Promoter Score is based on the response to the question, “How likely is it that you would recommend our device to a friend or colleague?” on a 5-point Likert scale.
 |

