4.2 SCIENTIFIC RATIONALE FOR STUDY DESIGN

Our main goal is to demonstrate $\geq 95\%$ adherence to ART in all patients across 90 days. Admittedly, this is a very high bar. However, we are confident that we will achieve it, even for patients who have problematic use. Our informal user testing to date has shown remarkable adherence rates with the HiDO device, and these have improved as we have moved into the current version (Version 3).

For participants who completely withdraw from the study before 90 days, adherence percentage will only be calculated for the time that they participated. While we will likely glean important information from those who do drop out early, these dropouts will not affect our primary endpoint calculation. We may also fail to recruit a pool of participants that reflects the diversity of the national HIV patient population. We expect, however, to be close, and will be able to recruit a sample sufficient to intelligently plan for larger scale future testing in diverse populations. If successful, we will have demonstrated that our automated medication adherence platform is highly usable, preliminarily enables strict adherence to ART, and is ready for larger scale testing in Phase II.

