6.1.2 DOSING AND ADMINISTRATION

The Principal Investigator will deliver the device to the participant's home and will assist each participant with initial device setup that includes filling the device with ART (the device holds and can dispense up to 7 different medications), installing the device app on the participant's smartphone, and configuring the device and app. The participant receives a smartphone alert when it is time to take a medication. The participant then pushes the button on the device and receives the correct medicine at the given time. In addition to tracking time, frequency, and other medication administration data, the

device video records the interaction to verify that the medication was consumed. If the patient does not respond, additional reminders are sent via SMS and read as: "It's time to take your morning medication" (for late doses scheduled for 12pm Pacific Time or earlier) or "It's time to take your evening medication" (for late doses scheduled after 12pm Pacific Time).

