9.3 POPULATIONS FOR ANALYSES

- Modified Intention-to-Treat Analysis Dataset: participants who are enrolled for at least 7 days of the 90-day intervention period
- Per-Protocol Analysis Dataset: participants who complete the 90-day intervention period and post-study interview and questionnaire.

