9.4.2 ANALYSIS OF THE PRIMARY EFFICACY ENDPOINT(S)

Given the small sample size and specification of secondary endpoints, descriptive statistics are sufficient to either accept or reject the null hypothesis.

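### No analysis set is named for the ≥95% adherence conclusion, and one sentence in Section 4.2 can be followed as leaving dropouts out of it

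*Combined protocol and SAP*

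**What the plan says.** - **Endpoint.** Section 3 gives "Mean adherence rate to ART in all patients across 90 days". The formula beside it has doses provided minus doses taken as numerator and ends in "n. of doses provided x 100". Section 4.2 repeats the all-patient, 90-day goal with the ≥95% threshold.
- **Withdrawals.** For complete withdrawals, Section 4.2 says "adherence percentage will only be calculated for the time that they participated". The next sentence says that "these dropouts will not affect our primary endpoint calculation".
- **Analysis sets.** Section 9.3 defines a modified ITT set, "participants who are enrolled for at least 7 days of the 90-day intervention period", and a per-protocol set, "participants who complete the 90-day intervention period and post-study interview and questionnaire". It does not rank them.
- **Decision.** Section 9.4.2 names no set. It says only that, with a small sample, "descriptive statistics are sufficient to either accept or reject the null hypothesis".
- **Expected loss.** Section 9.2 recruits 24 so that at least 15 complete, at 60% completion. Section 7.2 lists non-compliance with the intervention among the reasons for withdrawal and allows replacement to keep at least 15. Section 7.1 lets a participant stop the device and stay on study.

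**The concern.** The two sentences in Section 4.2 pull apart. If a leaver's partial data enter the mean, the leaver does affect the primary endpoint. The second sentence must therefore mean one of two things: time after withdrawal does not count, or leavers are left out. The two unranked sets in Section 9.3 match these two readings, and Section 9.4.2 does not choose between them.

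The conclusion rests on a descriptive figure set against a threshold, so the set, the window and the weighting are in effect the decision rule. About four in ten participants are expected not to complete, and poor compliance is itself a route out of the study, so it is plausible that leavers adhere less than stayers. At stake is whether this single-arm pilot reports ≥95% and, as Section 4.2 puts the consequence, moves on to larger-scale testing. No formal error rate is involved.

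**Working it through.** **1. The plan's own figures.** Section 9.2: 24 × 0.60 = 14.4 completers, against 15 stated. In reverse, 15/0.60 = 25 recruited, against 24 stated. Both agree to within one participant. A completers-only analysis would therefore omit 9 or 10 of 24.

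**2. Size of the difference.** Let n_L be the number of leavers, and A_C and A_L the mean adherence of completers and leavers, with each participant weighted equally.

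Completers-only mean − all-24 mean = (n_L/24) × (A_C − A_L)

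The multiplier is 9/24 = 0.375 or 10/24 = 0.417. If A_C = A_L, the difference is zero.

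**3. Illustration.** The documents give no adherence for leavers, so these values are assumptions: completers 96%, leavers 80%.

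| Leavers | Completers only | All 24, equal weight |
|---|---|---|
| 10 | 96.0% | (14×96 + 10×80)/24 = 89.3% |
| 9 | 96.0% | (15×96 + 9×80)/24 = 90.0% |
| 5 | 96.0% | (19×96 + 5×80)/24 = 92.7% |

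The last row covers the case where some non-completers use the device for 90 days and miss only the interview.

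**4. Range over leaver adherence.** Take 15 completers at exactly 95% and 9 leavers. The all-24 mean is 93.1% if leavers average 90%, 89.4% at 80%, 84.9% at 68% and 79.6% at 54%. The last two values are Section 9.2's baseline range, used here only as a low end.

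**5. Weighting.** Section 3 does not say whether the mean is per participant or pooled over doses. Assume once-daily dosing and leavers who stay to day 30:
- 10 leavers: (14×90×0.96 + 10×30×0.80)/(1260 + 300) = 1449.6/1560 = 92.9% pooled, against 89.3% with equal weight.
- 5 leavers: (1641.6 + 120)/1860 = 94.7% pooled, against 92.7%.
- 5 leavers who go at day 14: (1641.6 + 56)/1780 = 95.4% pooled, so the ≥95% conclusion would stand.

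For the all-24 figure to reach 95% in the day-30 case, leavers must average 93.6% (equal weight) or 90.8% (pooled) with 10 leavers, and 91.2% or 83.6% with 5.

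**6. End of the window.** The own-window rule gives no end date. Assume 19 participants at 96% and 5 who take 19 of 20 scheduled doses, stop, and give notice on day 27. Ending at last use: (19×96 + 5×95)/24 = 95.8%. Ending at notification: 19/27 = 70.4%, and (19×96 + 5×70.4)/24 = 90.7%. This gap exists only if the denominator is scheduled doses.

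**7. Formula.** With 90 doses provided and 86 taken, the printed expression gives (90 − 86)/90 × 100 = 4.4%, which is non-adherence. Taken over provided gives 86/90 × 100 = 95.6%.

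**The case against.** A reader might infer that the protocol plans a completers-only analysis and that a ≥95% result would therefore be biased. The documents do not support that. The own-window sentence would have little purpose for the primary endpoint if leavers were excluded, and Sections 3 and 4.2 both speak of all patients. Against these stands one loosely worded clause. This part of the objection stands: the defect is an unresolved ambiguity, and including partial data is the better-supported reading.

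A reader might also infer that the denominator counts only dispensed doses, because the participant "pushes the button on the device and receives the correct medicine at the given time", so that nothing is counted after last use. That is the weaker reading. Section 6.1.2 sends reminders when a scheduled dose is late, and Section 6.1.1 describes dashboards that show missed as well as taken pills. The platform evidently works from a schedule.

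The numerical examples rest on assumed leaver behaviour, and some leave the conclusion unchanged. The study is a descriptive pilot, and Section 9.4.8 tabulates individual data, so other sets could be recomputed. Both points are fair. They limit the claim about size, but they do not settle which figure carries the conclusion.

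Finally, counting every unlogged dose as missed would penalise participants who retrieve medication by hand when the device malfunctions, as Sections 2.2 and 2.3.3 allow. That is a good reason not to make it the primary rule.

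**Conclusion.** The concern holds as an ambiguity that should be fixed. No set is named as primary, and one sentence, if followed literally, gives a selected result. Excluding leavers would raise the reported mean by 0.375 to 0.42 times the completer-minus-leaver difference: 6.0 to 6.7 points if that difference is 16 points, and zero if there is none. That leavers adhere less is plausible, given the withdrawal reasons in Section 7.2, but the documents do not establish it.

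Confidence is high on the missing designation and on the inverted formula. It is low on the presence and size of any bias. Naming the 7-day set would reduce the problem without removing it: participants enrolled for under 7 days stay out, and an own-window mean still says nothing about adherence after withdrawal.

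**What to change.** 1. **Section 4.2:** delete the sentence saying that dropouts leave the primary calculation unaffected. Keep the own-window sentence.
2. **Sections 9.3 and 9.4.2:** name the 7-day modified ITT set as primary, including anyone later withdrawn or replaced. Replacements are added, not substituted. Make the per-protocol set supportive.
3. **Section 3:** correct the formula to doses taken / doses scheduled × 100, as a per-participant mean, with the pooled rate also reported.
4. **Window:** use one end date. This is day 90 or, for complete withdrawals, the notification date already used for payment in Section 5.5. Participants who stop the device but stay on study, and those lost without a notification date, are followed to day 90.
5. **Sensitivity analyses, not the primary rule:** unlogged doses counted as not taken; unlogged doses with documented malfunction or manual retrieval excluded; a full 90-day lower bound; and adherence by 30-day period. The team should state before data are seen how unlogged doses enter the primary figure.

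This changes who is analysed and how, not who may be withdrawn. The cost is wording in Sections 3, 4.2, 9.3 and 9.4.2, plus a few tables from data the device already logs. The downside is that the headline figure may be lower, and it may understate adherence where ART is taken off-device, most of all for participants who stop the device and stay on study.

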4.3 JUSTIFICATION FOR DOSE

Not applicable.

4.4 END OF STUDY DEFINITION

A participant is considered to have completed the study if he or she has completed all phases of the study including the last visit or the last scheduled procedure shown in the Schedule of Activities (SoA), Section 1.3.

5 STUDY POPULATION

5.1 INCLUSION CRITERIA

To be eligible to participate in this study, an individual must meet all the following criteria:

1. Provision of signed and dated informed consent form
2. Stated willingness to comply with all study procedures and availability for the duration of the study
3. Male or female, ages 18 and older
4. Prescribed at least one existing ART
5. Self-reported as taking less than 100% of ART does in past 30 days
6. Access to a personal smartphone and Wi-Fi connection

5.2 EXCLUSION CRITERIA

An individual who meets any of the following criteria will be excluded from participation in this study:

1. Changes to ART regimen within the previous 2 months
2. Anticipated changes to ART regimen during the study period
3. Illicit drug use within the past 6 months, excluding marijuana
4. Diagnosis of dementia of any type
5. Participation in a clinical study within the previous 3 months

Participants will be recruited without bias to gender/gender identity, race, ethnicity, religion, or sexual orientation from existing patient populations using anti-retroviral therapy.

Children have been excluded from the current study; while they stand to benefit from such a device and may be included in future study phases, the proposed sample size is not large enough to account for the possible influence of parents upon children's medication adherence. As both illicit drug use and dementia may also interfere with medication adherence in unanticipated ways, the current trial phase will exclude individuals self-reporting recent illicit drug use and/or a diagnosis of dementia; future trial phases may expand selection criteria to include these individuals. To maintain consistency in study conditions, individuals with recent or imminent changes to their ART regimen are also excluded.

5.3 LIFESTYLE CONSIDERATIONS

Not applicable.

5.4 SCREEN FAILURES

Screen failures are defined as participants who consent to participate in the clinical trial but are not subsequently assigned to the study intervention or entered in the study. A minimal set of screen failure information is required to ensure transparent reporting of screen failure participants, to meet the Consolidated Standards of Reporting Trials (CONSORT) publishing requirements and to respond to queries from regulatory authorities. Minimal information includes demography, screen failure details,

eligibility criteria, and any serious adverse event (SAE). Data from screen failures are retained as for other participant data (see Section 10.1.9.2).

Individuals who do not meet the criteria for participation in this trial (screen failure) because of access to a personal smartphone and Wi-Fi connection may be rescreened. Rescreened participants will be assigned the same participant number as for the initial screening.

5.5 STRATEGIES FOR RECRUITMENT AND RETENTION

The target sample will approximate the distribution of HIV/AIDS patients by race and ethnicity, and will equally enroll men and women, as seen in Figure 3.

Figure 3. Target sample by gender, race, and ethnicity.

| Racial Categories | Ethnic Categories | | | | Total | |
|--|------------------------|----------|--------------------|----------|-----------|--|
| | Not Hispanic or Latino | | Hispanic or Latino | | | |
| | Female | Male | Female | Male | | |
| American Indian/ Alaska Native | 0 | 0 | 0 | 0 | 0 | |
| Asian | 0 | 0 | 0 | 0 | 0 | |
| Native Hawaiian or Other Pacific Islander | 0 | 0 | 0 | 0 | 0 | |
| Black or African American | 5 | 5 | 0 | 0 | 10 | |
| White | 4 | 4 | 3 | 3 | 14 | |
| More than One Race | 0 | 0 | 0 | 0 | 0 | |
| Total | 9 | 9 | 3 | 3 | 24 | |

Participants will be recruited from the outpatient population of HIV/AIDS patients in the San Francisco Bay region of California; the study will not enroll participants outside of the United States. Potential participants will be recruited using a 1-page flyer that will be posted in one or more medical practices in the Bay Area that specialize in the prevention and treatment of HIV/AIDS; providers and staff of these practices are not otherwise affiliated with the study.

It is expected that approximately 75% of screened patients will be determined eligible for study enrollment, so approximately 32 individuals will be screened to reach the target sample size (n=24), which we expect to occur at a rate of approximately 2 participants per week.

To aid retention efforts, medication adherence for each participant is monitored through the HiDO platform. The HiDO unit is first and foremost a medication adherence device. The device will transmit real time data about adherence and trial participation. To maintain study integrity, we cannot intervene to promote adherence beyond the reminders and prompts provided by the medication adherence system. That said, having the device in the home is a powerful, indirect participant retention tool.

To compensate participants for their time, participants will receive \$100 gift card, which is disbursed upon return of the HiDO device. Participants who do not complete study receive \$5 for each full week

from device setup to date of notification by either party of study withdrawal, delivered by Visa gift card at device pickup.

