1.3 SCHEDULE OF ACTIVITIES (SOA)

| Procedures | Screening / baseline measurement Day -14 to -1 | Week 1, Day 1 (Completion of platform setup) | Week 2, Day 14 +/-1 day | Week 4, Day 28 +/-1 day | Week 6, Day 42 +/-1 day | Week 8, Day 56 +/-1 day | Week 10, Day 70 +/-1 day | Week 12, Day 84 +/-1 day | Week 13, Day 90 +/-1 day | Week 14, Day 97 +/-7 days |
|--|---|---|----------------------------|----------------------------|----------------------------|----------------------------|-----------------------------|-----------------------------|-----------------------------|------------------------------|
| Informed consent | X | | | | | | | | | |
| Demographics | X | | | | | | | | | |
| Medication adherence self-report | X | | | | | | | | | |
| Delivery of HiDO platform | X | | | | | | | | | |
| Assisted platform setup | X | | | | | | | | | |
| Time on Task | X | X | X | | | | | | X | |
| Error rate | X | X | X | | | | | | X | |
| Automated medication adherence | | X-----X | | | | | | | | |
| Device log audit | | | X | | X | | X | | | X |
| Usability assessment (semi-structured interview) | | | | | | | | | | X |
| Adverse event review and evaluation | | X-----X | | | | | | | | |
| Complete Case Report Forms (CRFs) | X | | | | | | | | | |

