Study Procedures: As part of screening procedures, participants complete a 10-minute medication adherence self-assessment via phone. The researcher will schedule a visit to the participant's home, expected to last approximately 45 minutes, to conduct consent process and set up the device. After conducting consent procedures and collecting participant demographic information, the researcher will deliver the HiDO device to each participant's home and assist each participant with platform setup, which includes loading ART medications into the dispenser (up to 7 different types), calibrating facial-recognition, and setting up the participant's smartphone to interact with the device. Following platform setup, participants use the HiDO platform for 90 days, which will provide notifications for, dispense, and monitor each participant's ART dosing. At the end of the 90-day intervention period, participants complete a semi-structured interview, administered via phone and lasting approximately 30 minutes, to assess device usability and complete post-intervention medication adherence self-assessment. Excluding screening, total study duration is 104 days +/- 7 days.

Data are collected for medication adherence and usability from the following sources:

1. Medication adherence:
 - a. Automated dosage logs generated by HiDO device
 - b. Manual audit of automated dosage logs
 - c. Pre- and post-study medication adherence self-assessment questionnaire
2. Usability:
 - a. Automated user logs generated by HiDO device
 - b. Post-study semi-structured interview
 - c. System Usability Scale
 - d. Net Promoter Score

Hypotheses:

Hypothesis 1: Use of the HiDO automated medication adherence platform will result in ≥95% medication adherence over 90 days.

Hypothesis 2: Usability scores for the HiDO platform (as measured by Time on Task for initial registration, “first click” testing, facial recognition setup, and medication administration, number and type of critical and non-critical errors, and error-free rate) will be equal to or better than published benchmark rates for similar platforms.

Hypothesis 3: The System Usability Scale (SUS) value for the HiDO platform will be equal to or better than published benchmark rates for similar platforms (>68).

Hypothesis 4: Greater than 80% of participants will indicate that they are Likely or Strongly Likely to recommend the HiDO device to a friend or colleague.

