6.2 PREPARATION/HANDLING/STORAGE/ACCOUNTABILITY

6.2.1 ACQUISITION AND ACCOUNTABILITY

At the beginning of the study, the HiDO medication adherence platform will be delivered in person to the home of record of each participant. At the end of the 90-day intervention period, the device will be picked up from the participant's home by the PI.

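### The full payment is tied to device return and not to the later interview that supplies SUS, endorsement and the post-study self-report, and a missed interview also removes a complete adherence log from the per-protocol set

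*Combined protocol and SAP*

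**What the plan says.** - **Payment (5.5).** Participants receive a $100 "gift card, which is disbursed upon return of the HiDO device". The sentence does not mention the interview. Those who do not complete the study get $5 per whole week, counted from setup to notice of withdrawal and handed over when the device is collected.
- **Pickup (6.2.1).** "At the end of the 90-day intervention period, the device will be picked up" from the home by the PI. The SoA has no row for device return.
- **Interview (1.3 and 4.1).** The SoA row "Usability assessment (semi-structured interview)" is marked only under "Week 14, Day 97 +/-7 days". Section 4.1 words the timing differently: "At the end of the 90-day intervention period, participants complete a semi-structured interview, administered via phone". The same call serves "to assess device usability and complete post-intervention medication adherence self-assessment".
- **What depends on it (9.1).** Secondary endpoints 3 (SUS) and 4 (endorsement) are analysed once the post-intervention interview is done. Neither has its own SoA row.
- **Completion (4.4).** A participant has finished only when everything in the SoA has been done, which includes the interview.
- **Analysis sets (9.3).** Per-protocol means "participants who complete the 90-day intervention period and post-study interview and questionnaire". The modified ITT set needs only 7 days of enrolment.

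**The concern.** Section 5.5 itself credits the device in the home with helping retention. On the nominal schedule both that help and the payment have ended before the interview call. Hypotheses 3 and 4 and the post-study adherence self-report all rest on that call, so the plan risks losing data from people who did everything else.

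There are two knock-on problems. The payment text does not settle what is owed to someone who finishes device use and then misses the call. And 9.3 makes the interview a condition of the per-protocol set, although the adherence endpoint comes from the device. A full 90-day log can then leave that analysis for a reason unrelated to dosing.

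The stakes are higher because 9.4.3 lets descriptive results alone accept or reject the secondary hypotheses, and no analysis rule covers a missing interview.

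**Working it through.** **1. Order of events.** Take pickup as Day 90 (6.2.1 gives no exact day). The interview window in 1.3 runs from 97 − 7 = Day 90 to 97 + 7 = Day 104. The gap from pickup to interview is nominally 97 − 90 = 7 days, with a range of 0 to 14 days. Payment comes first on the nominal schedule; a same-day interview is possible.

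**2. Amount in doubt.** Reading 4.4 into 5.5, a participant who misses the interview has not completed and falls to the weekly rate.
- Counted to Day 90: 12 whole weeks × $5 = $60, so $100 − $60 = $40 is in doubt.
- Counted to Day 97: 13 × $5 = $65, so $35.
- Counted to Day 104: 14 × $5 = $70, so $30.

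Reading 5.5 alone, $100 was due at device return. The documents do not choose between these readings.

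**3. The plan's own completion figure.** Section 9.2 has 24 enrolled and 60% completing: 24 × 0.60 = 14.4, against a stated minimum of 15. Worked backwards, 15 / 0.60 = 25, close to the stated 24. Under 4.4 those 15 have already given the interview, so a further interview loss should not be subtracted from them. Below, 15 is only an assumed number of people who finish the device period.

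**4. Hypothesis 4 (more than 80% endorse).** The number of missed interviews is assumed; the documents give no rate.

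| Situation among 15 device completers | Result | >80%? |
|---|---|---|
| All interviewed, 12 endorse | 12/15 = 80.0% | No |
| One of the three non-endorsers is missing | 12/14 = 85.7% | Yes |
| Three missing, 10 of 12 endorse | 10/12 = 83.3% | Yes |
| Same, missing counted as non-endorsers | 10/15 = 66.7% | No |
| Same, missing counted as endorsers | 13/15 = 86.7% | Yes |

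One selective non-response is enough to change the conclusion.

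**5. Per-protocol adherence.** As an assumed case, 12 per-protocol participants average 95%, and three with full 90-day logs but no interview average 80% to 90%.
- At 80%: (12 × 95 + 3 × 80) / 15 = 92%.
- At 90%: (12 × 95 + 3 × 90) / 15 = 94%.

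The per-protocol mean would meet the 95% target, while the mean over everyone with a full log would not. If the three had the same adherence as the rest, nothing would shift.

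**The case against.** The strongest reply is that the documents do not fix the order. The interview window opens on Day 90, 4.1 and 6.2.1 describe interview and pickup with the same timing phrase, and 5.5 gives no date for device return. That stands: the defect is an order left open whose nominal form is unfavourable, not a schedule that forces payment first.

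Other points also stand in part:
- **Safeguards exist.** Section 7.3 requires contact attempts after a missed interview: where possible three calls, and a certified letter if needed. Section 7.2 allows replacement to keep at least 15. These reduce loss, but they do not restore the incentive or say how a missing interview is analysed.
- **The interview is part of compliance in 6.4**, so its place in a per-protocol definition is not arbitrary. It still says nothing about whether a device log is complete.
- **Small numbers are imprecise anyway.** The exact lower 95% limit is about 52% for 10/12 and 59.5% for 13/15, so most of the uncertainty is present with no interview loss.

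A reader might infer three stronger things that the documents do not support. One is that the payment rule cannot work: the weekly rate is written for people who withdraw during device use, and someone who only misses the later call is simply not addressed. Another is that primary-endpoint data are lost: the modified ITT set keeps these logs, and 4.2 uses even partial data from withdrawals. The third is that interview loss will be sizeable and selective: no rate is given and nothing shows who would be missing.

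**Conclusion.** The point holds on the nominal schedule. Full payment depends on device return only, and the contact that supplies Hypotheses 3 and 4 and the post-study self-report is nominally a week later. Day 90 Time on Task and error rates and the Week 14 log audit are separate SoA items and are not affected.

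The payment text is ambiguous by about $30 to $40 per affected participant, and 4.4 and 5.5 should be reconciled. The effect on adherence is confined to the per-protocol set; whether it touches the primary conclusion depends on which set is primary, which is not stated.

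The amount of interview loss is unknown, so the figures above show sensitivity and are not forecasts. With about 15 respondents and a descriptive >80% rule, a single missing non-endorser can turn a failure into a success. That justifies a change of wording that is this cheap.

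**What to change.** 1. **Sections 5.5 and 1.3.** Release the card once both device return and the interview with questionnaire are done. Alternatively, hold the phone interview before pickup, inside its existing window. Add a device-return row to 1.3 so that the order is fixed.
2. **Sections 4.4 and 5.5.** State what is paid to someone who finishes 90 days of use but not the interview.
3. **Section 9.3.** Define the per-protocol set for adherence by completion of the 90-day device period. Require the interview only for Hypotheses 3 and 4. Name the set that is primary for the adherence endpoint.

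The cost is wording in these sections, a matching consent line, and slightly later payment for some participants. No extra visit or participant is needed.

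Collecting SUS and the endorsement item face to face at pickup would also close the gap, but should be avoided. The PI collects the device, and asking for ratings in person with payment pending invites favourable answers. Keep the ratings on the phone, and say in the consent form that payment depends on completing the interview and not on the answers.
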